12.5. Safety Monitoring

Investigators will report all serious adverse events to the Sponsor within 24 hours of identification. The Sponsor and Medical Monitor(s) will promptly review information relevant to the safety of the device or drug. All serious and all unanticipated adverse device or drug-related events will be reviewed within 24 hours of Tusker Medical awareness. The Investigator is responsible for reporting events to the IRB according to IRB requirements, and the Sponsor is responsible for reporting to regulatory authorities according to regulatory requirements.

If the Sponsor determines that study participation poses a significant risk to subjects, the sponsor shall suspend or discontinue the study and notify regulatory authorities, investigators and IRBs as appropriate.

[figure not shown]
Adverse Events will be adjudicated as deemed appropriate by the Medical Monitor(s). The Medical Monitor(s) will review all AEs and their coding for accuracy and consistency periodically.

A large black rectangular redaction box covers the top portion of the page, from approximately the top third to the middle. A smaller black rectangular redaction box is located at the bottom center of the page.

12.6. Device Malfunctions

Any inadequacy of the device or packaging with respect to its identity or performance will be recorded as a device malfunction. Information regarding the device identity (eg, device name/code and lot number), temporal aspect of the malfunction (eg, prior to opening, during preparation during procedure), nature of the malfunction and relatedness to potential adverse events will be collected on appropriate CRFs.

13.0 STATISTICAL METHODS

This pivotal study intends to evaluate effectiveness and safety of iontophoresis using the IPS and TDS for TT placement in-office for children indicated for tympanostomy tube placement (the pivotal cohort). The study also includes subjects enrolled into OR lead-in and in-office lead-in cohorts.

The pivotal phase of the study aims to confirm safety, and determine whether the in-office tube placement procedure achieves acceptable procedural success and tube placement tolerability rates. The pivotal cohort will consist of a sample of 222 children with evaluable data including 102 children age 5 to 12 years old, and 120 children less than 5 years of age. There are two primary endpoints for the pivotal cohort: (1) Procedural Success will be the proportion of subjects with Tusker Medical tympanostomy tubes placed in all indicated ears in an office procedure, and (2) Tube Placement Tolerability will be the mean subject-reported pain score following TDS tube placement using the Faces Pain Scale-Revised

(FPS-R) (children ages 5 and older only). The statistical tests for the co-primary endpoints are hypothesis tests against performance goals. Further details regarding the statistical methods may be found in the Statistical Analysis Plan CPR007004 which includes an appended Adaptive Design Report describing the primary endpoint statistical model and operating characteristics.

13.1. General Statistical Methods

Descriptive statistics will be provided. Data collected in the study will be summarized overall and as defined in the protocol.

Routine presentation of continuous variables in descriptive tables will include mean, standard deviation, sample size, and median. Categorical or binary variables will be presented with numerator, denominator, and percent.

The SAS system (v9.2 or later) or R Statistical package (3.2.1 or higher) will be used to perform all statistical analyses.

13.2. Analysis Sets

13.2.1. Full Analysis Set

All subjects in whom the lidocaine is introduced into the ear canal and for whom iontophoresis was initiated will be included in the FAS.

13.2.2. Per Protocol Set

The Per Protocol Set is a subset of the FAS and includes all FAS subjects without major protocol deviations. Major protocol deviations include:

- Eligibility violations
- Procedural deviations with the potential to affect anesthesia efficacy (eg, abbreviation of iontophoresis or use of incorrect local anesthesia drug).

13.2.3. Safety Analysis Set

The Safety Analysis Set will include all pivotal cohort subjects in whom the lidocaine solution is introduced into the ear canal.

13.3. Primary Endpoint Analysis

Procedural Success: The proportion of subjects in the pivotal cohort FAS achieving procedural success will be evaluated against a performance goal of 68%. The study design employs a Bayesian hierarchical gatekeeper strategy whereby the test against the performance goal occurs in two steps:

- 1) The initial test against the performance goal is conducted on the older children in the pivotal cohort, once the study has accrued evaluable data for 102 children ages 5 through 12 years of age.

The primary hypothesis is

Test 1:

$$H_0: p_{5+} \leq 68\%$$

vs.

$$H_a: p_{5+} > 68\%$$

Where p_{5+} is the proportion of subjects 5 through 12 years old achieving procedural success.

This hypothesis will be tested using a Bayesian hierarchical model evaluating whether the posterior probability of H_a is at least 0.975, which is analogous to a classical hypothesis test at the 0.025 significance level in the FAS comprising only subjects 5 through 12 years old. This Bayesian analysis applies the test to the older group, while borrowing data from all enrolled evaluable subjects less than 5 years old, as appropriate given the performance results at the time of the first test. [REDACTED]

[REDACTED] If the older group achieves the performance goal, the second test is applied to the younger subjects as described in step 2. [REDACTED]

- 2) The final test for the procedural success primary endpoint is applied once the full pivotal cohort is enrolled (102 older subjects in Test 1, plus 120 younger subjects ages 6 months to less than 5 years old). The second test evaluates the younger subjects against the performance goal while borrowing data from the 102 older subjects using a Bayesian hierarchical model as appropriate given the performance of the older group.

Test 2:

$$H_0: p_{<5} \leq 68\%$$

vs.

$$H_a: p_{<5} > 68\%$$

Where $p_{<5}$ is the proportion of subjects in the younger group (6 months through <5 years old) achieving procedural success.

Test 2 is also performed using a Bayesian hierarchical model, requiring a 97.5% posterior probability of H_a . [REDACTED]

[REDACTED]
[REDACTED]
[REDACTED]
[REDACTED]
[REDACTED]

Tube Placement Tolerability: Mean subject-reported pain score following TDS tube placement using the Faces Pain Scale-Revised (FPS-R). The mean pain score for

subjects in the pivotal cohort FAS, for whom tube placement was successful, will be evaluated against a performance goal of 4.2 pain score.

The test against the performance goal is conducted on only the older children in the pivotal cohort, once the study has accrued evaluable data for 102 children ages 5 through 12 years of age.

The primary hypothesis is

$$H_0: p_{5+} \geq 4.2$$

vs.

$$H_a: p_{5+} < 4.2$$

Where p_{5+} is the mean Tube Placement FPS-R for subjects 5 through 12 years old.

This hypothesis will be tested using a standard classical t-test at the 0.025 significance level in the FAS comprising only subjects 5 through 12 years old. Tube Placement

13.4. Secondary Efficacy Endpoint Analyses

Secondary endpoints will be tested on the 102 older children upon successful achievement of the primary endpoints. If the 102 older children pass the test, a gatekeeper design will be employed and the secondary endpoints will be tested on the full pivotal cohort once enrolled (102 older children plus 120 younger children). The secondary endpoints (Tube Patency, Tube Retention and Anesthesia Effectiveness) are functions of the tube and iontophoresis device performance and are not anticipated to vary by subject age. Therefore, testing the secondary endpoints on the full (pooled) pivotal cohort is appropriate.

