11.4.7. Anesthesia Effectiveness

Following iontophoresis, the Investigator will use physician judgment to assess whether the TM is adequately anesthetized for the tympanostomy tube placement procedure by evaluating subject response to a gentle tap of the TM with a dull otologic instrument,

The tap will occur on the anterior half of the TM at the location where the tympanostomy tube will be placed. This tap assessment method has been used successfully in prior studies to determine adequate anesthesia for subsequent tympanostomy tube placement for both children and adults.

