11.4.8. Tolerability (FPS-R)

The Faces Pain Scale-Revised (FPS-R) (**Figure 10**) is an instrument for assessing procedural pain validated for use in children 4 years of age and older. This study will employ the FPS-R for children in the older cohort only (age 5 years and greater). Subjects ages 5 years and older will rate their discomfort following TDS tube placement (after second ear, if bilateral treatment) using the FPS-R. If optional suction is performed, the subject will rate their discomfort following suction of both ears (if indicated bilaterally). In addition, an FPS-R score will be collected from the children approximately 5 minutes after completion of tube placement, or after completion of suction (whichever intervention is last). A baseline measure of ear discomfort will be assessed after ear cleaning (if required) and prior to Earset placement.

[figure not shown]

Figure 10. Faces Pain Scale-Revised

If a subject discontinues the procedure prior to completion of tube placement, an FPS-R score will be collected for the discontinued procedure.

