11.4.9. Tolerability (FLACC)

The FLACC (Face, Legs, Activity, Cry, Consolability) scale is a method to evaluate behavioral distress for children as young as 2 months or individuals that are unable to communicate their pain.⁶¹ The FLACC is a valid and reliable pediatric observational measure that ranges from low (0) to high (10) distress. The FLACC is recommended in the PedIMMPACT consensus statement and is a widely used observational measure of pediatric behavioral pain and distress.⁶²

The scale has five categories which are each assigned a score of 0, 1 or 2 by an evaluator, as shown in **Table 3**.

Table 3. FLACC Scoring

Category	Score 0	Score 1	Score 2
Face	No particular expression or smile	Occasional grimace or frown, withdrawn, uninterested	Frequent to constant quivering chin, clenched jaw
Legs	Normal position or relaxed	Uneasy, restless, tense	Kicking, or legs drawn up
Activity	Lying quietly, normal position, moves easily	Squirming, shifting, back and forth, tense	Arched, rigid or jerking
Cry	No cry (awake or asleep)	Moans or whimpers; occasional complaint	Crying steadily, screams or sobs, frequent complaints
Consolability	Content, relaxed	Reassured by occasional touching, hugging or being talked to, distractible	Difficult to console or comfort

FLACC scoring will be performed using the videos of the children's procedures, and will evaluate distress observed in the 6 procedural phases: pre-procedure otoscopy, iontophoresis earset installation/earset filling, iontophoresis, eardrum tap/tube placement, suction if suction is performed, post-procedure. A FLACC score will also be assigned to the overall procedure. Trained video evaluators (coders) at a centralized core lab (to ensure consistency in grading) will code a randomly selected sample of the study videos to assess interrater reliability to assess agreement across all 5 FLACC categories. █

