15.1. Subject Stopping Criteria

Subjects who do not complete the study procedure, will be encouraged to remain in the study to complete post-procedure evaluations. If a subject withdraws prematurely from the

study, a genuine effort must be made to determine the reason(s) why the subject failed to return for the procedure or follow-up visit or discontinued the study, and the reason must be recorded on the appropriate CRF.

Potential reasons for discontinuation include:

- Subject or subject's caregiver decides it is in the subject's best interest to withdraw
- Subject expresses intolerance or discomfort during the procedure and subject or subject's caregiver indicates they wish to stop the procedure and withdraw
- Investigator decides if a serious adverse event requires withdrawal from the study
- Investigator decides it is in the subject's best interest to be withdrawn if subject is experiencing intolerance or intolerable reaction to the procedure.

If a subject discontinues participation in the study, the Investigator will attempt to have the subject continue participation to complete follow-up assessments unless the subject's safety is compromised. All Serious Adverse Events that have not resolved by the end of the subject's participation in the study, must be followed until the event resolves, stabilizes or becomes non-serious.

All potential subjects in the study will be verbally informed and will sign an informed consent in compliance with 21CFR §50 that states that any withdrawal from the study will neither prejudice nor in any way affect their future treatment.

Prior to designating a subject as lost to follow-up, the site must provide documented evidence of three (3) good faith attempts to contact the subject to which there has been no response. At that point the subject will be considered lost-to-follow-up and withdrawn from the study.

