11.0 Secondary Endpoint Analyses

[REDACTED]

[REDACTED]

[REDACTED]

[REDACTED]

[REDACTED] The secondary endpoints (Tube Patency, Tube Retention and Anesthesia Effectiveness) are functions of the tube and iontophoresis device performance and are not anticipated to vary by subject age. Therefore, the second test on the full (pooled) pivotal cohort is appropriate.

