17.0 Sensitivity Analyses and Handling of Missing Data

The number and proportion of subjects eligible for and compliant with all follow-up examinations will be presented. Subjects who withdraw from the study will be tabulated with the reasons for the withdrawal. Subjects who initiate the procedure, regardless of tolerability outcome or anesthesia effectiveness, will be encouraged to return for all follow-up assessments.

For the Procedural Success primary endpoint, all subjects who initiate iontophoresis are included in the primary analysis of this primary endpoint. Therefore, no missing data analyses for the Procedural Success primary endpoint are planned.

For the Tube Placement Tolerability primary endpoint, all subjects in the pivotal cohort FAS for whom tube placement was successful are included in the primary analysis of this primary endpoint. [REDACTED]

Tube Retention secondary endpoint: Tube Retention is the proportion of subjects in the pivotal cohort FAS, in which a Tusker Medical tube was successfully placed, with presence of a Tusker Medical tube across the tympanic membrane in all successfully treated ears at the 3-week post-procedure follow-up visit. Subjects missing the 3-week follow-up visit will not be included in the Tube Retention secondary analysis.

Tube Patency secondary endpoint: Tube Patency is the proportion of subjects in the pivotal cohort, in which a Tusker Medical tube was successfully placed, with a functionally patent tube in all successfully treated ears at the 3-week post-procedure follow-up visit. Subjects missing the 3-week follow-up visit will not be included in the Tube Patency secondary analysis.

[REDACTED]

[REDACTED]

[REDACTED]

[REDACTED]

Anesthesia Effectiveness secondary endpoint: Anesthesia Effectiveness is the proportion of subjects in the pivotal cohort FAS, who completed iontophoresis for all indicated ears, with adequate anesthesia for tympanostomy tube placement in all treated ears as determined by physician's evaluation of TM anesthesia prior to tube placement. Subjects who complete iontophoresis but do not complete TM tap assessment for all indicated ears will be counted as failures. [REDACTED]

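### Does counting an uncompleted eardrum tap as an anesthesia failure undermine the reason given for pooling Anesthesia Effectiveness across ages?

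*Protocol*

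**What the plan says.** Protocol 13.4 tests Tube Patency, Tube Retention and Anesthesia Effectiveness first on the 102 older children and then on the full pivotal cohort of 102 plus 120. Its reason for pooling is that the three endpoints "are functions of the tube and iontophoresis device performance and are not anticipated to vary by subject age". SAP 11.0 gives the same reason and concludes: "Therefore, the second test on the full (pooled) pivotal cohort is appropriate".

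Anesthesia Effectiveness (Protocol 13.4.3, SAP 11.3) is the proportion adequately anesthetized in all treated ears among Full Analysis Set children who completed iontophoresis in all indicated ears. It is tested by mid-P against 85% and needs p below 0.025. Under Protocol 11.4.7 the physician judges adequacy "by evaluating subject response to a gentle tap of the TM with a dull otologic instrument".

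SAP 17.0 adds the scoring rule for incomplete assessments: "Subjects who complete iontophoresis but do not complete TM tap assessment for all indicated ears will be counted as failures". The visible text around the rule makes no exception for cause. Text directly after it, and at the opening of SAP 11.0, is blacked out.

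**The concern.** A child can receive the full charge in every indicated ear and then refuse the tap. The rule scores that child as an anesthesia failure although anesthesia was never fully assessed. The endpoint therefore mixes what the device did with whether the child accepted the next step, and the second part could depend on age.

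The protocol gives some grounds for that suspicion. Protocol 15.1 lists as a reason to discontinue: "Subject expresses intolerance or discomfort during the procedure". On self-reported pain, Protocol 11.4.8 says: "This study will employ the FPS-R for children in the older cohort only". Protocol 11.4.9 describes an observer scale for very young children and for "individuals that are unable to communicate their pain". Procedural Success, by contrast, is modelled with a separate probability for each age group.

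If under-5 children left more taps uncompleted, a pooled result could mislead in two ways. A device that works equally well at both ages could miss the goal because of refusals. Or strong results in older children could carry the pooled test while the under-5 rate sat below 85%. The visible text has no separate under-5 test of this endpoint.

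**Working it through.** The visible text states no expected rate or power for this endpoint, so there is no planned figure to reproduce. What can be checked is how the pooled test behaves under assumed rates.

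**Inputs from the documents.** Goal 85%; one-sided mid-P below 0.025; n = 102 older, then n = 222 pooled. These sizes are upper limits, because only children completing iontophoresis in all indicated ears are counted.

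**Critical counts.** With X ~ Binomial(n, 0.85), mid-P(r) = P(X > r) + 0.5 × P(X = r).

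- n = 102: mid-P is 0.0165 at 94 and 0.0351 at 93, so 94 are needed (92.2%).
- n = 222: mid-P is 0.0229 at 199 and 0.0366 at 198, so 199 are needed (89.6%).

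**Assumed model.** Let d be the share adequate among children tapped, equal at both ages. Let q be the share of under-5 children whose tap is not completed, with none in older children. The older rate is d and the under-5 rate is d × (1 − q). The under-5 rate falls below 85% when q exceeds 1 − 0.85/d:

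- d = 93%: 1 − 0.85/0.93 = 8.6%
- d = 95%: 1 − 0.85/0.95 = 10.5%
- d = 97%: 1 − 0.85/0.97 = 12.4%

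**Chance the endpoint is met** (older count at least 94 and pooled count at least 199, by exact binomial summation):

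| d | q = 0 | q = 5% | q = 10% | q = 15% |
|---|---|---|---|---|
| 93% | 0.713 | 0.591 | 0.239 | 0.039 |
| 95% | 0.930 | 0.899 | 0.587 | 0.165 |
| 97% | 0.996 | 0.995 | 0.897 | 0.455 |

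**Chance it is met while the observed under-5 rate is below 85%:**

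| d | q = 0 | q = 5% | q = 10% | q = 15% |
|---|---|---|---|---|
| 93% | 0.000 | 0.008 | 0.024 | 0.011 |
| 95% | 0.000 | 0.007 | 0.066 | 0.057 |
| 97% | 0.000 | 0.002 | 0.094 | 0.190 |

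For this second event the under-5 count must be 101 or fewer (0.85 × 120 = 102), so the older count must be at least 199 − 101 = 98 of 102. If 2% of older children also leave the tap uncompleted, then at d = 95% and q = 10% the chance of meeting the endpoint is 0.388 and the second event falls from 0.066 to 0.022.

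**What limits q.** Inclusion criterion 3 requires a cooperative temperament for the awake procedure. Protocol 11.4.4 makes children who are uncooperative during the screening ear exam and cleaning ineligible. Protocol 10.10 lets the investigator exclude or reschedule a child for behavior on the procedure day. Every child in the denominator has already sat through iontophoresis, about 10 minutes without interruptions (Protocol 11.7.5). On the tap itself, Protocol 11.4.7 states: "This tap assessment method has been used successfully in prior studies", for both children and adults.

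**What an uncompleted tap means.** The rule covers all indicated ears. A child with two indicated ears whose first tap hurts, and who is not tapped in the second, fails because of inadequate anesthesia. Some uncompleted taps are therefore device failures, in line with the pooling rationale.

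**The case for a change.** The strongest case for a change is that the rationale is inaccurate as worded for one of the three endpoints and costs little to correct. Cooperation screening may lower non-completion but does not show that it is equal across ages. The requirement that the older children pass first gives no protection against a lower rate in the 120 younger ones. Patency and retention treat missing assessments the opposite way, by leaving out children who miss the 3-week visit, so the shared rationale fits anesthesia least well. Reasons for uncompleted taps are best recorded at the time, which argues for specifying them in advance.

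Much of this stands. The sentence is loose, and under-5 results for this endpoint are easier to interpret if uncompleted taps are shown apart from inadequate anesthesia. What does not follow is a need to alter the plan. The sentence states an expectation about age, and a conservative scoring rule contradicts it only if non-completion differs by age, which no section says. The larger effect in the tables is a lower chance of success, which works against the sponsor. Under-5 evidence does not rest on this endpoint: Procedural Success is tested separately in that group, and an uncompleted tap that leaves an indicated ear without a tube is a failure there. Pain from inadequate anesthesia that prevents tube insertion is recorded as an adverse event (Protocol 11.7.7), reasons for discontinuation are summarized (SAP 7.0), and all case report form data are listed by subject (SAP 21.0). An analyst could split the failures by age and type largely from those data.

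**Conclusion.** No change to the plan is called for. The pooled test is valid for the pooled proportion. Counting uncompleted taps as failures is a defensible rule that avoids crediting the device with unassessed anesthesia. The price is some loss of interpretability, and that is a fair trade-off.

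The misleading outcome, a met endpoint with an under-5 estimate below 85%, has probability 0.002 to 0.008 at 5% under-5 non-completion and 0.024 to 0.094 at 10%. It reaches 0.190 only at 15% with d = 97%. These figures assume full denominators, equal device performance at both ages and no uncompleted taps in older children. The rates are illustrative, since the documents give none.

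Rewording the rationale and tabulating the endpoint by age, with uncompleted taps and their reasons shown separately, would be a reasonable reporting choice. Taps stopped because the first ear hurt should be identifiable in such a table. It would leave the test, the 85% goal, the failure rule and the success condition as they are. Redacted parts of SAP 11.0 and 17.0 may already contain it. The point does not extend to patency or retention.

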13.4.1. TUBE PATENCY

Tube Patency is the proportion of subjects in the pivotal cohort FAS, in which a Tusker Medical tube was successfully placed, with functional tube patency in all successfully treated ears at the 3-week post-procedure follow-up visit.

The statistical test for the pivotal cohort Tube Patency secondary endpoint is a hypothesis test for the proportion of subjects with functional tube patency in all successfully treated ears at the 3-week follow-up visit against a tube patency performance goal. The mid-P^{71,72,73} method for a single proportion will be used to test

$$H_0: p \leq 80\%$$

Vs.

$$H_a: p > 80\%.$$

This endpoint will be considered met if the p-value from the test is less than 0.025.

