7.0 Subject Disposition

Subject disposition will be summarized with counts and percentages. Categories summarized will include the number of subjects who signed informed consent, number of screen failures (with reasons), and the number enrolled, completed, and discontinued, as well as reasons for discontinuation. The summary of disposition will also include the number and percentage of subjects included in each analysis set described in Section 6, and for each age strata and cohort.

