8.0 Demographic Characteristics and Medical History

Demographic characteristics including age, sex and race/ethnicity will be descriptively summarized for all enrolled subjects in each of the defined study cohorts. Significant medical history will also be summarized for all enrolled subjects in each of the defined study cohorts. Demographic characteristics and medical history will be presented separately for each of the Analysis Sets defined for the Pivotal Cohort, and for each age strata.

[REDACTED]

[REDACTED]

[REDACTED]

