14.3 Audiometric Assessments

Change in audiometric measurements (shifts) from baseline to the 3-week follow-up visit for subjects in the Safety Analysis Set will be presented using descriptive statistics (mean, SD, median, minimum and maximum). Shifts in air conduction (AC) and bone conduction (BC) hearing thresholds will be reported for each frequency (500, 1000, 2000 and 4000 Hz, and air conduction only at 8000Hz) and for each Cohort on a by-ear basis (treatment ears only). Shifts from baseline to each follow-up visit in air-bone gap (air conduction minus bone conduction) will also be reported for each frequency (500, 1000, 2000 and 4000 Hz) for each Cohort on a by-ear basis. Shifts in air conduction pure tone average (AC PTA), bone conduction PTA (BCA) and air-bone gap averages will be presented for each follow-up time point for each Cohort. For all PTA measurements, the PTA will be calculated by adding the threshold levels in decibels (dB) obtained at each frequency tested divided by number of frequencies tested.

Shift tables for air conduction pure tone averages greater than 15 dB (>15dB) by ear will be calculated, and presented for each Cohort for each follow-up time point.

Degree of hearing loss severity will be defined according to the protocol (slight through profound) and presented by subject for each Cohort and by relationship to study device, procedure or study drug.

Due to the differences in audiometric requirements for children dependent on age, all audiometry results will be presented by subjects less than 4 years of age, greater than 4 years of age, and overall.

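### Does pooling the under-5s with older children who have already passed make the second test of the secondary endpoints unsound?

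*Protocol*

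**What the plan says.** Protocol 13.4 sets a sequence for the three secondary endpoints. They are tested on the 102 older children once the primary endpoints are met. If that succeeds, "a gatekeeper design will be employed and the secondary endpoints will be tested on the full pivotal cohort once enrolled", which means 102 older plus 120 younger children. The reason given is that the endpoints reflect tube and device performance and "are not anticipated to vary by subject age". The section concludes: "Therefore, testing the secondary endpoints on the full (pooled) pivotal cohort is appropriate". SAP 11.0, whose opening lines are redacted, reaches the same place: "Therefore, the second test on the full (pooled) pivotal cohort is appropriate".

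The individual hypotheses are on a single proportion with no age term. Protocol 13.4.1 is typical: "The statistical test for the pivotal cohort Tube Patency secondary endpoint is a hypothesis test for the proportion of subjects". The goals are 80% for patency, 88% for retention and 85% for anesthesia effectiveness. Each uses a mid-P test and is met if p is below 0.025 (Protocol 13.4.1 to 13.4.3; SAP 11.1 to 11.3).

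Age is a named reporting dimension elsewhere in the SAP. Disposition is given by analysis set "and for each age strata and cohort" (7.0). Demographics and history are given "for each of the Analysis Sets defined for the Pivotal Cohort, and for each age strata" (8.0). For hearing, "all audiometry results will be presented by subjects less than 4 years of age, greater than 4 years of age, and overall" (14.3).

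**The concern.** The primary endpoint of procedural success has its own under-5 hypothesis (Test 2 in Protocol 13.3). The secondary endpoints do not. Their second test reuses 102 children who have already cleared the goal, 102/222 = 46% of the sample, so the younger children need not clear it themselves. The bridge from a pooled pass to a statement about under-5s is the premise that age does not matter, and the visible text names no under-5 rate that would check it.

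The premise is open to question. Anesthesia effectiveness is a physician's judgement of a child's response to a tap on the eardrum (Protocol 11.4.7), and under SAP 17.0 an incomplete tap assessment counts as a failure, so cooperation may enter the result. If older children did much better, the pooled p-value would hide it, and a reader could credit under-5s with a goal they had missed.

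**Working it through.** The visible text gives no power, assumed rate or pass mark for these endpoints, so there is no design figure to reproduce beyond 102 + 120 = 222, which agrees.

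**Inputs.** Goals, alpha and mid-P method come from Protocol 13.4.1 to 13.4.3; group sizes come from 13.4. Age-specific true rates are assumptions. So is full evaluability: patency and retention drop children without a placed tube or a 3-week visit. A reduced split of 82 older and 90 younger is used as a check.

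**Pass marks.** For x successes in n with goal g, one-sided mid-P = P(X > x) + 0.5 × P(X = x), X ~ Bin(n, g). The pass mark is the smallest x with mid-P below 0.025.

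| Endpoint | Goal | Older, n = 102 | Pooled, n = 222 | Pooled mid-P at mark |
|---|---|---|---|---|
| Patency | 80% | 90 | 190 | 0.0163 |
| Anesthesia | 85% | 94 | 199 | 0.0229 |
| Retention | 88% | 96 | 205 | 0.0191 |

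**How low can under-5s be?** The lowest passing under-5 count is the pooled mark minus the older count.

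- If the older group only just clears its own test: patency 190 − 90 = 100/120 (83.3%), anesthesia 199 − 94 = 105/120 (87.5%), retention 205 − 96 = 109/120 (90.8%). All are above goal.
- Smallest observed gap that passes with under-5s at or just below goal: patency 94/102 against 96/120 (92.2% − 80.0% = 12.2 points); anesthesia 97/102 against 102/120 (95.1% − 85.0% = 10.1); retention 100/102 against 105/120 (98.0% − 87.5% = 10.5).
- Worked example: patency 97/102 and 93/120 totals 190/222 and passes. The under-5 rate is 77.5% (mid-P 95% CI 69.4% to 84.3%). The two age groups then differ with a two-sided Fisher p of 0.0002.

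**Chance of passing both steps.** Sum over older counts o at or above the older mark: P(older = o) × P(younger ≥ pooled mark − o). Under-5s are exactly at goal, n = 102/120.

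| Older advantage over goal | Patency | Anesthesia | Retention |
|---|---|---|---|
| 0 points | 0.006 | 0.008 | 0.009 |
| 2 points | 0.02 | 0.03 | 0.03 |
| 3 points | 0.03 | 0.04 | 0.05 |
| 5 points | 0.07 | 0.12 | 0.14 |
| 7 points | 0.16 | 0.25 | 0.30 |
| 10 points | 0.36 | 0.54 | 0.62 |

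At 82/90 the 10-point row is 0.33, 0.39 and 0.52, and the zero row is 0.007 to 0.008. The low values at 2 to 3 points arise mainly because the older-only step itself passes only 6% to 18% of the time.

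With under-5s truly 3 points below goal, the chance is 0.010, 0.014 and 0.014 if older children are 3 points above it, and 0.06, 0.09 and 0.10 if they are 7 points above.

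**If the premise holds.** With equal rates in both groups (90% patency, 92% anesthesia, 95% retention), a full pass combined with an observed under-5 rate at or below goal has probability under 0.1% for each endpoint. Replacing the pooled test by an under-5-only second test would cut full-sequence power from 0.78 to 0.67, from 0.56 to 0.36 and from 0.75 to 0.56, respectively.

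**The case for a change.** The best case for a change is that it costs almost nothing. One table of rates and intervals for under-5s and for ages 5 to 12 needs no new data, alpha or sample size. The SAP already breaks other outputs down by age, and Protocol 6.1 puts 58% of tube procedures in children under 5, so readers will want that group's result. A rate that can be worked out is not the same as a pre-specified one with an interval, and the chances of 0.36 to 0.62 at a 10-point advantage are not small.

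Part of this stands: a pooled pass alone does not show that under-5s meet the goal, and the arithmetic is correct. But the large probabilities need a true age gap for which the documents give no figure. The visible text does not present the pooled test as an under-5 test; it words each hypothesis for the pivotal cohort, which is the limited claim one would ask for. The first test supplies the 5-to-12 counts, so subtracting them from the pooled counts gives the under-5 numerator and denominator exactly. SAP 21.0 also lists the data for every child. Finally, redaction covers the opening of SAP 11.0, the text after SAP 11.3 and the Protocol text after 13.4.3. These are natural homes for a by-age summary, so its absence from the visible pages does not establish a gap.

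**Conclusion.** No change to the plan is needed. Followed as written, it gives a sound conclusion about the whole pivotal cohort, and when both age groups sit at goal the two-step procedure passes less than 1% of the time. Pooling is a fair trade-off: it keeps power, rests on a stated reason, and follows a test that the older children must pass alone. It could mislead about under-5s only if a reader took the whole-cohort result as theirs while older children did about 10 or more observed points better, a gap that the counts from the two tests would reveal.

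The size of the concern depends on assumed age-specific rates and denominators; at a 2 to 3 point older advantage, with under-5s at goal, the chance of passing both steps is 0.02 to 0.05. What remains is a reporting preference. If the redacted text lacks it, analysts would sensibly print the under-5 rate with a mid-P 95% interval beside each pooled result and rest any under-5 statement on that estimate.
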